1.3. Statistical Hypotheses

The primary hypothesis of this study is that the experimental treatment ibrutinib + obinutuzumab compared with chlorambucil + obinutuzumab will significantly improve PFS in subjects diagnosed with CLL or SLL who are treatment-naive but now require active therapy.

The statistical hypotheses are as follows:

H_0 : The PFS distributions of experimental treatment group, $S_I(t)$, and the control group, $S_C(t)$, are equal at all time points t :

$$S_I(t) = S_C(t), \text{ for all } t > 0$$

versus

H_1 : The PFS distributions of experimental treatment group, $S_I(t)$, are different from the control group, $S_C(t)$, at at least one time point t :

$$S_I(t) \neq S_C(t), \text{ for some } t > 0$$

These hypotheses will be tested using a 2-sided stratified log-rank test at α level of 0.05.

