1.6. Testing Procedure and Level of Significance

To preserve the study wise type I error rate of 0.05, the primary and secondary endpoints will be tested based on a serial gatekeeping testing procedure at the two-sided significance level of 0.05 according to the hierarchical order as listed in 1.2.2.

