4. ANALYSIS FOR ENDPOINTS

Analysis of endpoints will be conducted on the ITT population, unless otherwise specified. Table 1 summarizes the efficacy endpoints and analysis methods to be performed.

The following two randomization stratification factors will be used for the stratified analysis/test: ECOG performance status (0, 1 versus 2) and Cytogenetics (del 17p, del 11q without del 17p, others). To reflect the randomization process and maintain the integrity of randomization, all stratified tests will be based on randomization stratification factors as recorded in the IWRS.

For subgroup and exploratory analysis, only the analysis that provide meaningful information will be presented.

Table 1: Definitions and Analyses for Endpoints

Endpoint	Definition	Analysis Method
Primary Endpoint		
PFS assessed by IRC	Time from the date of randomization to the date of IRC-assessed disease progression or date of death from any cause, whichever occurred first, regardless of the use of subsequent antineoplastic therapy prior to documented PD or death.	
Primary Treatment effect of ibrutinib plus obinutuzumab compared to chlorambucil plus obinutuzumab was tested with a log-rank test. The hazard ratio and its 95% CI based on a Cox regression model are calculated. PFS distribution is estimated by Kaplan-Meier method: median PFS and landmark estimates with 2-sided 95% CIs are to be provided for each treatment arm.
 
Sensitivity Analyzing PFS assessed by investigator using the same method as PFS assessed by IRC.
 
Subgroup Hazard ratio and its 95% CI based on unstratified Cox regression model for each subgroup.

Secondary Endpoints		
PFS assessed by IRC in high risk analysis set	Defined the same as the primary endpoint.	Analyzed the same as primary endpoint in high risk analysis set
ORR assessed by IRC	The proportion of subjects achieving a best overall response of CR, CRi, nPR, or PR per IRC assessment at or prior to initiation of subsequent antineoplastic therapy.	Chi-square test.
Overall survival (OS)	Time from the date of randomization to the date of death from any cause. All deaths observed at the time of the analysis will be considered as events. For subjects who were not known to have died at the time of the analysis, OS data will be censored at date last known alive.	Analyzed the same as PFS primary analysis.

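### Does SAP Table 1 leave open whether the PFS and OS analyses are stratified?

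*SAP*

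**What the plan says.** - **SAP 1.3**, on the primary PFS hypothesis: "These hypotheses will be tested using a 2-sided stratified log-rank test", at a level of 0.05.
- **SAP 4, text above Table 1**: "The following two randomization stratification factors will be used for the stratified analysis/test". It then names ECOG (two levels) and cytogenetics (three levels), with values taken from the IWRS.
- **SAP 4, Table 1, primary row**: "Treatment effect of ibrutinib plus obinutuzumab compared to chlorambucil plus obinutuzumab was tested with a log-rank test" and "The hazard ratio and its 95% CI based on a Cox regression model are calculated". Neither sentence states whether strata are used.
- **Table 1, subgroup entry**: "Hazard ratio and its 95% CI based on unstratified Cox regression model for each subgroup".
- **Table 1, high-risk PFS**: "Analyzed the same as primary endpoint in high risk analysis set". **OS**: "Analyzed the same as PFS primary analysis".
- **SAP 1.6**: "the primary and secondary endpoints will be tested based on a serial gatekeeping testing procedure", in the order of SAP 1.2.2. High-risk PFS is the first of the eight secondary endpoints and OS is the fifth.
- **Protocol 10.7.1** names a log-rank test and a Cox model and leaves the detail of the model to the SAP. Protocol 10.7.2.3 says OS is handled in a similar way to PFS.

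**The concern.** Table 1 is where a programmer looks for the method, and the key adjective is missing there. Neither document literally calls the primary Cox model stratified, or the high-risk PFS and OS analyses. A literal reader of the table could report a stratified p-value beside an unstratified hazard ratio, or run the two secondary tests without strata.

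High-risk PFS is the most exposed. It is a small set, and failing it ends formal testing of the seven endpoints behind it. In an open-label trial one wants every confirmatory test fixed in advance, since choosing between two versions afterwards would raise the error rate.

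Region looks like a second loose end. It defines the two randomisation schemes in SAP 1.7.2, but it is not among the factors for the stratified test.

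**Working it through.** **1. The planned size does not depend on the choice.** Inputs from SAP 1.4: HR 0.55, two-sided 5%, 80% power, 1:1 allocation.

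- Freedman: events = ((1 + 0.55)/(1 − 0.55))² × (1.960 + 0.842)² = 11.86 × 7.85 = 93.1, so 94. This is the plan's figure. Power at 94 events is 80.4%.
- Schoenfeld: 4 × 7.85/(ln 0.55)² = 31.40/0.3574 = 87.8, so 88. Power at 94 events is 82.6%.

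Neither formula has a term for strata, so the 94 events and 212 subjects are the same under both readings.

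**2. What the text fixes.**

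| Analysis | Where it is settled | Reading |
|---|---|---|
| Primary PFS test | SAP 1.3, with factors and source in SAP 4 | Stratified, stated outright |
| Primary hazard ratio | SAP 4 text refers to a stratified analysis as well as a test; Table 1 marks only the subgroup model unstratified | Stratified, by inference |
| High-risk PFS, OS | Table 1 says they follow the primary analysis, which SAP 1.3 stratifies | Stratified, by inheritance |

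Table 1 is introduced as a summary, so its shorter wording does not undo SAP 1.3. Labelling the subgroup model unstratified would be pointless if the main model were unstratified too. Most of the other comparisons are plain chi-square tests, so the log-rank tests and Cox models are the natural objects of the stratification paragraph.

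**3. Size for primary PFS if strata were left out.** Two simulations used the SAP 1.4 design (212 subjects, 18 per month, 94 events, HR 0.55, Arm B median 27 months). Both take del 17p at 10% from Protocol 1.1.3. All prognostic effects and the remaining prevalences are assumed.

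*Simulation A*: 3,000 trials per setting, del 11q 20%, ECOG 2 10%, no dropout, region ignored. Monte Carlo standard error near 80% power is √(0.8 × 0.2/3000) = 0.7 points.

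| Prognostic HR (del 17p/del 11q/ECOG 2) | Power, stratified vs not | Verdicts differ | Average HR, stratified vs not | Null rejection, stratified vs not |
|---|---|---|---|---|
| 1/1/1 | 81.8 vs 82.0% | 2.7% | 0.546 vs 0.546 | 4.4 vs 4.1% |
| 2/1.5/1.5 | 81.2 vs 80.1% | 4.4% | 0.553 vs 0.561 | 5.1 vs 4.7% |
| 4/2/2 | 79.9 vs 75.1% | 7.5% | 0.547 vs 0.577 | 5.3 vs 3.7% |
| 6/2.5/2.5 | 80.7 vs 72.9% | 10.4% | 0.543 vs 0.592 | 4.9 vs 2.6% |

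*Simulation B*: 20,000 trials per setting, del 11q 15%, ECOG 2 7%, region 35/65, blocks of 4 within the 12 randomisation cells. The strong setting uses 3/1.8/1.8, with 1.5 for region. Stratified vs unstratified power was 81.8 vs 82.2% with no prognostic effect, 81.0 vs 81.5% with moderate effects, 79.6 vs 77.6% with strong effects, and 92.0 vs 91.4% with strong effects where del 17p is prognostic in Arm B only. Verdicts differed in 2.5 to 6.0% of trials.

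Across both, stratified minus unstratified power runs from −0.5 points (81.0 − 81.5) to +7.8 points (80.7 − 72.9). So the test named in SAP 1.3 costs almost nothing at worst and gains when strata are prognostic. An unstratified hazard ratio would lie nearer 1, which understates the benefit.

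**4. High-risk PFS and OS (Simulation B).** With 5% TP53 mutation without del 17p (Protocol 1.1.3), the high-risk set is about (10 + 5 + 15)% × 212 = 64 subjects, with 28 to 40 events. OS uses Protocol 10.7.2.3: 229 subjects, 33 deaths, HR 0.39. The six-stratum test has 0.9 to 2.4 points less power than the unstratified test for high-risk PFS, and 0.7 to 1.2 points less for OS. Verdicts differ in 7.7 to 10.0% and 3.1 to 4.9% of trials. Each test alone rejects in 4.1 to 5.2% under the null. Taking whichever is significant gives 6.2 to 6.4% for high-risk PFS.

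**5. Region.** SAP 1.7.2 treats region as defining two schemes and lists ECOG and cytogenetics as the factors within each; SAP 4 says two factors. With region there would be 2 × 2 × 3 = 12 cells. Under Simulation B's prevalences the four ECOG 2 cells with del 17p or del 11q expect 0.5, 0.8, 1.0 and 1.4 of 212 subjects; for example, 212 × 0.07 × 0.35 × 0.10 = 0.5. Adding region lowers power by 0.3 to 1.0 points for PFS, 0.5 to 0.7 for OS and 1.5 to 2.5 for high-risk PFS.

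**The case for a change.** The strongest contrary case is that inference is not pre-specification. The protocol defers to the SAP, so the SAP is the only place where the hazard ratio model and the two secondary tests can be settled, and it never uses the word for them.

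For high-risk PFS the inheritance is also less tidy than for OS. The set is defined by central laboratory results and includes TP53 mutation (SAP 2.1). The strata come from the IWRS and have no TP53 level, so subjects with only a TP53 mutation fall in the residual cytogenetic stratum. Whether six strata suit about 64 subjects is a fair question, and a few words would answer it.

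What stands is that the adjective is absent and that the two versions can disagree near the threshold. What does not stand is that the analysis is open. The high-risk test is said to follow a primary analysis that SAP 1.3 stratifies, and the IWRS strata exist for every randomised subject, so it can be run as written. A stratum with few subjects contributes little information but does not invalidate the test. Using fewer strata would recover at most about 2.4 points of power under these assumptions, which is a matter of preference. The inflated figure of 6.2 to 6.4% requires running both versions and picking one, which means departing from the stated inheritance.

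**Conclusion.** The plan can stand. The primary PFS test is fixed in SAP 1.3. For the primary hazard ratio, high-risk PFS and OS, the missing adjective in a summary table is a gap that analysts would fill in one sensible way, with the strata given directly above it. Leaving region out is a stated choice, and the power figures favour it.

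Validity is not at stake: in these runs null rejection was between 2.6% and 5.3% whichever test was used. The power consequence for high-risk PFS and OS is at most about 2.4 points, and it slightly favours the unstratified test. These figures rest on assumed prevalences of del 11q and ECOG 2, an assumed region split and assumed prognostic effects. The two simulations differ in size under strong effects, with verdicts on PFS differing in up to 10.4% of trials in one and 6.0% in the other. The conclusion does not hinge on that spread, because the reading of the SAP comes from its text and the sample size is the same either way. Adding the adjective to the table would be harmless editing and would not alter the analysis to be run.

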The results of clinical studies in previously untreated CLL have demonstrated major advances in therapy over the last decade. The most active regimen described thus far, on the basis of a single-center experience at the MD Anderson Cancer Center (Keating 2005) and subsequent randomized CLL8 trial (Hallek 2010), is the chemoimmunotherapeutic combination of fludarabine, cyclophosphamide and rituximab (FCR). Although numerous subsequent attempts have been made to improve on FCR eg, through the addition of mitoxantrone, alemtuzumab or granulocyte macrophage colony-stimulating factor (Parikh 2011; Bosch 2009; Reynolds 2012), increasing the dose of rituximab (FCR3) (O'Brien 2005), substituting cladribine or pentostatin for fludarabine (Wierda 2012; Bryan 2011), or combining rituximab with bendamustine (Fischer, 2012) so far this remains the most active regimen and regarded as a standard of care for fit first line patients (Hillmen 2010a).

Despite the impressive disease control demonstrable with FCR and FCR-like regimens in optimally selected patient populations, CLL remains a disease predominantly of the elderly, or those with other concomitant medical conditions, who are less able to tolerate fludarabine based approaches. There is, therefore, a clinical need to continue exploration of new treatment options for older patients and those with multiple co-morbidities (Dores 2007; Gribben 2009).

Additionally, CLL is both pathologically and clinically heterogeneous, resulting in many patient sub groups who respond markedly less favorably to currently available treatment strategies, independently of age and comorbidity. In particular, one feature which has consistently been associated with the worst overall prognosis is deletion of the short arm of chromosome 17 (del 17p) and/or a mutation of the TP53 tumor suppressor gene. These abnormalities occur in about 7-10 % of CLL cases at diagnosis (Krober 2002) and this patient subgroup is characterized by rapid disease progression, poor response to therapy and a very limited median overall survival of less than three years (Dohner 2000).

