### **1.1.3. Chronic Lymphocytic Leukemia with 17p Deletion and/or TP53 mutation**

Apart from age and co-morbidity, a number of intrinsic genetic and molecular abnormalities have been characterized which also identify subgroups of CLL patients who generally have an adverse clinical course and a poor outcome to therapy. These include del 17p, del 11q, IgVH unmutated status, use of the IGHV3-21 gene segment and expression of either ZAP70 or CD38 (Krober 2002; Krober 2006). However, it is widely acknowledged that chromosomal 17p deletion is the pre-eminent adverse prognostic parameter, with the majority of patients belonging to an “ultra-high-risk” group characterized by the worst possible overall outcome (Stilgenbauer 2010).

Approximately 10% of patients with CLL in the first line treatment setting carry the del 17p abnormality (Dohner 2000). As the TP53 tumor suppressor gene, which plays a critical role in oncogenesis and response to DNA damaging chemotherapy (Hollstein 1991; Pietsch 2008) is located on the short arm of chromosome 17, over eighty per cent of del 17p deletions are also associated with concomitant p53 dysfunction of some sort (Rossi 2009).

The associated loss of p53 integrity may explain why the del 17p abnormality is the poorest prognostic factor for CLL. So integral in fact is the del 17p/TP53 axis to determining chemoresponsiveness in CLL, that it has been postulated as the only biomarker currently available for driving treatment decisions in the management of the disease (Mertens 2014).

The presence of a TP53 mutation can however also occur in the absence of a del 17p chromosomal abnormality, in approximately five percent of cases of CLL (Rossi 2009; Dicker 2009) and is an equally poor prognostic factor, independent of 17p status (Zenz 2008; Oscier 2002).

Both 17p deletion and TP53 mutation are therefore powerful prognostic markers for non-response to currently available CLL therapy. Patients with these abnormalities have exceptionally poor outcomes with chemoimmunotherapy regimens such as FCR, due in large part to lack of p53 function, which is an important pathway for mediating the cytotoxicity of many drugs, including purine analogs, such as fludarabine (Dohner 1995).

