## 4. SUBJECT SELECTION

### 4.1. Inclusion Criteria

#### *Disease Related*

1. Diagnosis of CLL/SLL that meets IWCLL diagnostic criteria (Hallek 2008).
2. Age 65 yrs and older OR if less than 65 years old, must have at least one of the following criteria:
  - a. Cumulative Illness Rating Score (CIRS)  $> 6$ .
  - b. Creatinine clearance estimated  $< 70$  mL/min using the Cockcroft-Gault equation.
  - c. Del 17p by FISH or TP53 mutation by PCR or Next Generation Sequencing (NGS).
3. Active disease meeting at least 1 of the following IWCLL criteria (Hallek 2008) for requiring treatment:

- a. Evidence of progressive marrow failure as manifested by the development of, or worsening of, anemia (hemoglobin <10 g/dL) and/or thrombocytopenia (platelets <100,000/ $\mu$ L).
  - b. Massive ( $\geq 6$  cm below the left costal margin), progressive, or symptomatic splenomegaly.
  - c. Massive nodes (at least 10 cm longest diameter), or progressive or symptomatic lymphadenopathy.
  - d. Progressive lymphocytosis with an increase of more than 50% over a 2-month period or a lymphocyte doubling time (LDT) of <6 months. LDT may be obtained by linear regression extrapolation of absolute lymphocyte counts obtained at intervals of 2 weeks over an observation period of 2 to 3 months. In patients with initial blood lymphocyte counts of <30,000/ $\mu$ L, LDT should not be used as a single parameter to define indication for treatment. In addition, factors contributing to lymphocytosis or lymphadenopathy other than CLL (eg, infections) should be excluded.
  - e. Autoimmune hemolytic anemia and/or immune thrombocytopenia that is poorly responsive to corticosteroids or other standard therapy (see Exclusion Criteria 4).
    - Autoimmune hemolytic anemia is defined by at least one marker of hemolysis (indirect bilirubin above the upper limit of normal (ULN) not due to liver disease, increased lactate dehydrogenase (above ULN) without alternative etiology, or increased absolute reticulocytosis (above ULN) or bone marrow erythropoiesis in the absence of bleeding) AND at least one marker of direct or indirect autoimmune mechanism (positive direct antiglobulin for IgG or C3d, cold agglutinins) (Ding 2007).
    - Immune thrombocytopenia is defined by platelets  $\leq 100,000/\mu$ L and increased megakaryocytes on the bone marrow exam.

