### **10.7.2. Secondary Endpoints and Methods**

#### **10.7.2.1. Overall Response Rate**

Overall response rate (ORR) is defined as the proportion of subjects who achieve a CR, CRi, nPR, or PR, over the course of the study as evaluated by the IRC using IWCLL 2008 criteria, with modification for treatment-related lymphocytosis. Subjects who do not have any post-baseline response assessment will be considered as nonresponders. A chi-square test will be used to compare the two treatment arms.

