#### **10.7.2.2. Rate of Minimal Residual Disease (MRD)-negative Responses**

A chi-square test will be used to compare the rate of MRD-negative responses between the two treatment arms.

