1.7.2. Randomization Method

Central randomization will be implemented in this study. Two randomization schemes will be generated: one for each geographic region (North America versus Rest of World). Under each scheme, subjects will be randomized based on the following stratification factors:

- ECOG 0-1 vs 2
- Cytogenetics - will be stratified into one of three categories
 1. del 17p
 2. del 11q without del 17p
 3. others (neither del 17p nor del 11q)

Subjects will be randomized in a 1:1 ratio to either Treatment Arm A or Treatment Arm B within each randomization stratum. This randomization scheme will be implemented within the Interactive Web Response System (IWRS).

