Rate of MRD-negative response	Proportion of subjects who achieved MRD-negative response defined as < 1 CLL cell per 10,000 leukocytes as assessed by flow cytometry of a bone marrow aspirate or peripheral blood sample per central laboratory.	Chi-square test for MRD-negative response rate by bone marrow

- Rate of infusion related reactions will be analyzed using a Chi-square method.
- Rate of sustained platelet improvement will be analyzed using a Chi-square method
- Rate of clinically meaningful improvement in EQ-5D-5L utility score will be analyzed using a Chi-square method

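### Optional improvement: test ORR and MRD-negative response with a CMH test on the cytogenetic strata instead of a plain chi-square test; it costs almost nothing and may gain some power

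*SAP*

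**What the plan says.** SAP Table 1 (section 4) gives a plain chi-square test for ORR and "Chi-square test for MRD-negative response rate by bone marrow". The protocol matches it: "A chi-square test will be used to compare the two treatment arms" for ORR (10.7.2.1) and "A chi-square test will be used to compare the rate of MRD-negative responses between the two treatment arms" (10.7.2.2). None of these mentions strata.

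SAP 1.7.2 stratifies randomisation by ECOG (0-1 vs 2) and by cytogenetics: "Cytogenetics - will be stratified into one of three categories" (del 17p; del 11q without del 17p; others), under separate schemes by region. SAP section 4 states "The following two randomization stratification factors will be used for the stratified analysis/test", naming ECOG and cytogenetics as recorded in IWRS, but does not list which tests are stratified. Only the PFS log-rank test is explicitly called stratified (SAP 1.3).

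SAP 1.6 tests the secondary endpoints in the order of SAP 1.2.2 at two-sided 0.05: high-risk PFS, sustained hemoglobin improvement, MRD-negative response, ORR, OS, then three more.

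**The concern.** When arms are balanced within strata that predict the outcome, the between-stratum part of the variance drops out of the treatment comparison. The plain chi-square test still counts it in its standard error. It then rejects too rarely under the null and loses power.

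The documents give some reason to expect predictive strata. Protocol 1.1.3 describes del 17p as a strong marker of non-response to existing therapy, which bears on Arm B, and lists del 11q among the adverse markers. Protocol 1.1.4 points the other way for Arm A, expecting ibrutinib activity not to depend on del 17p. No passage links the strata to hemoglobin, platelets, infusion reactions or EQ-5D-5L, so the point is limited to ORR and MRD.

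The stake is the test order. A missed MRD or ORR test stops formal testing of OS and every later endpoint.

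**Working it through.** **The plan's own figure.** The documents state no power for ORR or MRD. The stated figure nearby is 94 PFS events for 80% power at HR 0.55, two-sided 5%, 1:1. It reproduces: by Freedman, z = √94 × (1 − 0.55)/(1 + 0.55) − 1.96 = 0.85, power 80.4%. It is not affected by this point.

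**Inputs from the documents.** 1:1 allocation; N = 212 (sample size sections) and 229 (protocol 10.7.2.3); two-sided 0.05. For the del 17p share, protocol 1.1.3 says "Approximately 10% of patients with CLL in the first line treatment setting carry the del 17p abnormality" and protocol 1.1 says "These abnormalities occur in about 7-10 % of CLL cases at diagnosis" of del 17p and/or TP53 mutation. Inclusion criterion 2c admits subjects under 65 on del 17p or TP53 mutation alone, so the trial share may be higher; 7% to 18% was covered.

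**Assumptions.** Response rates by stratum, del 11q 18%, ECOG 2 10%, North America 35%, treatment log odds ratio 0.85 (0.75 for MRD-like rates).

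**Closed-form check, strong pattern.** Arm B rates 30/75/85% in shares 10/18/72%, n = 106 per arm, ECOG left out.

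- Arm B overall: 0.10×0.30 + 0.18×0.75 + 0.72×0.85 = 0.777. At log odds ratio 0.85, Arm A is 50.1/87.5/93.0%, overall 0.877. Difference D = 0.100.
- Within-stratum variance: Arm B Σw·p(1−p) = 0.1466, Arm A 0.0916. True SD of D = √[(0.1466 + 0.0916)/106] = 0.0474.
- Standard error used by chi-square: √[2 × 0.827 × 0.173/106] = 0.0520. Used by CMH, pooling within strata: 0.0480.
- Power = Φ[(D − 1.96·SE)/SD]: chi-square 48.6%, CMH 55.1%.
- Null rejection of chi-square: √(0.1466/0.1733) = 0.920, where 0.1733 = 0.777 × 0.223. So P(|Z| > 1.96/0.920) = 3.3%.

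**Simulation.** 200,000 trials per scenario, permuted blocks of 4 in the 12 region × ECOG × cytogenetics cells, uncorrected chi-square. Power (%) at N = 212, del 17p 10%, chi-square → CMH on cytogenetics:

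| Arm B rates | Common odds ratio | Arm A flat across strata |
|---|---|---|
| 30/75/85% (strong) | 50.4 → 56.8 | 50.3 → 51.6 |
| 50/72/80% | 63.3 → 64.5 | 63.1 → 63.1 |
| 60/75/80% | 62.6 → 62.9 | 62.3 → 62.1 |
| 75% throughout | 65.8 → 65.4 | – |
| MRD-like 5/20/35% | 69.3 → 71.3 | 68.8 → 68.8 |
| MRD-like 15/20/25% | 69.0 → 69.1 | 68.8 → 68.5 |
| MRD-like 20% throughout | 67.2 → 67.0 | – |

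Power changes quoted in whole-range form come from unrounded results and can differ by 0.1 point from subtraction in this table.

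- Null rejection: chi-square 3.5-3.6% in the strong pattern and 4.5-5.1% otherwise; CMH 4.9-5.0%.
- Del 17p share 7% to 18%: change -0.3 to +3.1 points outside the strong common-odds-ratio case, up to +9.6 in it.
- 95% CI half-width for the risk difference, N = 212: 10.2 → 9.4 points in the strong pattern (coverage 96.2% → 94.8%), 12.7 → 12.4 for 5/20/35%, unchanged with no stratum effect.
- A separate simulation, with effects set for about 80% chi-square power and other assumed rates, gave +0.3 to +0.9 (MRD-like), +1.1 to +2.8 (ORR-like), +3.8 to +7.2 (very strongly prognostic) and 0.0 (not prognostic).

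**Earlier tests in the sequence.** If the high-risk set holds 40 PFS events (assumed), Schoenfeld power is Φ[(√40/2)·|ln HR| − 1.96]: 47.2% at HR 0.55, 71.4% at 0.45, 91.3% at 0.35.

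**The case against.** Chi-square is valid, prespecified and consistent across both documents, and nothing in SAP section 4 requires the binary endpoints to be stratified. That stands: this is a choice between two valid tests.

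The largest gains need a common odds ratio, which puts Arm A at about 50% response in del 17p against 93% in the others group. Protocol 1.1.4 expects roughly equal ibrutinib response with and without del 17p, and a flat Arm A leaves almost nothing outside the strong pattern. This stands and limits the expected size. Gains shrink further if the treatment effect is larger: with Arm A ORR of about 91-94%, inside the 83-95% that protocol 3.2.1 reports for ibrutinib with an anti-CD20 antibody, the 50/72/80% pattern gains only 0.0 to 0.4 point.

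The strata may also predict less well than assumed. IWRS values may rest on local FISH up to 180 days old (protocol 7.1.3.4), and TP53 mutation without del 17p, about 5% of cases (protocol 1.1.3), is not a stratum. The weaker patterns in the table cover this.

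Dropping ECOG departs from the factor pair named in SAP section 4. That is true, but using six strata lost up to 1.4 points and leaves about 212 × 0.10 × 0.10 ≈ 2 subjects with ECOG 2 and del 17p. One clarifying sentence settles it.

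Finally, both tests sit behind high-risk PFS and hemoglobin, so the realised benefit is smaller than the power changes shown. None of these arguments shows a material cost from CMH.

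**Conclusion.** The point holds as an optional improvement, not a correction. CMH on the cytogenetic strata restores the null rejection rate to about 5%. It lost at most 0.3 point of power in any scenario run (seven rate patterns, common or flat Arm A effect, four del 17p shares, two sample sizes).

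The gain is possible, not assured: about zero if Arm A response is flat across strata and the strata are not strongly prognostic, up to about 2 points in the moderate common-odds-ratio patterns at 10% del 17p, and 6 points or more only if cytogenetics is very strongly prognostic in both arms. All of this rests on assumed stratum rates and an assumed del 11q share, because the documents give neither. Confidence in the size is medium.

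**What to change.** In SAP Table 1, test ORR and MRD-negative response with a CMH test stratified by cytogenetics as recorded in IWRS (three strata), and report the Mantel-Haenszel risk difference with its 95% CI. Because SAP section 4 names two factors, add a sentence saying that these binary endpoints use cytogenetics only, with ECOG optional. Align protocol 10.7.2.1 and 10.7.2.2, or record the departure in the SAP. The other binary secondary endpoints can keep chi-square, or use the same test for consistency. Fix the choice before database lock.

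Two wording points can be settled in the same edit; they are separate from the case for CMH. Table 1 omits the word stratified for the log-rank test and the Cox model, although SAP 1.3 specifies a stratified log-rank test. And SAP section 4 gives no test for sustained hemoglobin improvement, second in the secondary order; the test for sustained improvement stands only in protocol 10.7.2.4.

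The cost is SAP text and a standard software option. The smallest stratum is expected to hold 212 × 0.10 ≈ 21 subjects (95% range 13 to 30), enough for CMH. The 94 events and 212 subjects do not change.
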